#### 10.2.3.1 Recording a Serious Adverse Event

When the diagnosis of an SAE is known or suspected, the Investigator should record the diagnosis or syndrome as the primary SAE term, rather than as signs or symptoms. Signs and symptoms may then be described in the event description. For example, dyspnea should not be used as an SAE term if the diagnosis, which caused the dyspnea, is known to be malignant pleural effusion.

Death should not be recorded as an SAE, but as an outcome of a specific SAE, unless the event preceding the death is unknown. In the exceptional case where the events leading to death are unknown, then death may be used as an event term. If an autopsy was performed, the autopsy the autopsy report should be provided.

### 10.2.3.2 Reporting a Serious Adverse Event

#### RESPONSIBILITIES OF THE INVESTIGATOR

Any death, SAE, or pregnancy, experienced by the subject after informed consent through the last study visit, regardless of relationship to study drug, must be promptly reported (within 24 hours of the Investigator becoming aware of the event) by telephone or electronic transmission to the Sponsor (or designee).

Contact information for SAE reporting:

Medpace Clinical Safety  
Medpace SAE hotline:  
Telephone: PPD [redacted] dial P or PPD [redacted] dial P  
Facsimile: PPD [redacted] or PPD [redacted]  
e-mail: PPD [redacted]

Additionally, the Investigator will be able to contact the **Medical Monitor**:

#### Medical Safety Contact

PPD [redacted]  
Phone (EU): PPD [redacted] extension PPD [redacted]  
Mobile phone: PPD [redacted]  
Email: PPD [redacted]

The Investigator will report the SAE to his or her IRB in accordance with IRB's standard operating procedures and policies. Adequate documentation must be maintained showing that the IRB was properly notified.

SAEs must be recorded on the SAE form in the electronic data capture (EDC) system. This requirement includes all SAEs that occur after informed consent through the last study visit. The minimum information required for SAE reporting includes identity of investigator, site number, subject number, an event description, SAE term(s), onset date, the reason why the event is serious (ie, the seriousness criteria), and the Investigator's assessment of the relationship of the event to study treatment. Additional SAE information including medications or other therapeutic measures used to treat the event, action taken with the study treatment due to the event, and the outcome/resolution of the event will be recorded. Paper forms for reporting SAEs will be provided to the study sites as back-up in case the EDC system is not accessible.

In all cases, the Investigator should continue to monitor the clinical situation and report all material facts relating to the progression or outcome of the SAE. Furthermore, the Investigator may be required to provide supplementary information as requested by the Sponsor (or designee).

## **RESPONSIBILITIES OF THE SPONSOR (OR DESIGNEE)**

The Sponsor (or designee) will process and evaluate all SAE as soon as the reports are received. For each SAE received, the Sponsor will decide as to whether the criteria for expedited reporting have been met.

The Sponsor (or designee) is responsible for promptly informing the FDA and other regulatory authorities as well as other participating Investigators of the event. Written submission must be made by the Sponsor to the FDA as soon as possible and in no event later than 15 calendar days after the Sponsor's initial notification of the event, or for an event that is fatal or life-threatening no later than 7 calendar days after the Sponsor's initial notification.

### **EXPEDITED REPORTING**

Under FDA ruling (US Code of Federal Regulations, Title 21 CFR Part 312.32) and the ICH Guideline "Clinical Safety Data Management: Definitions and Standards for Expedited Reporting E2A," the Sponsor is required to submit written documentation, in the form of a safety report, detailing:

- Any event associated with the use of the drug, that is both serious and unexpected, or
- Any finding from tests in laboratory animals that suggests a significant risk for human subjects, including reports of mutagenicity, teratogenicity, or carcinogenicity.

The Sponsor will submit SAEs that meet the criteria for expedited reporting to the regulatory authorities in accordance with local regulations governing safety reporting.

#### **10.2.4 Follow-Up of Adverse Events and Serious Adverse Events**

Any SAE or AE must be followed until either resolution of the event or determination by the Investigator that the event has become stable or irreversible. Appropriate diagnostic tests should be performed and therapeutic measures, if indicated, should be instituted until the event has returned to baseline or until a clinically satisfactory resolution has been achieved. The appropriate follow-up visits must be scheduled and the specific tests repeated or performed as necessary. The status of all AEs will be documented as of the last study visit. If all required information is not available at the time of the initial report, follow-up information will be completed in the EDC system.

### **10.3 Warnings and Precautions**

#### **10.3.1 Vaccinations**

Subjects must not receive any vaccinations from within 2 weeks of screening until 28 days following final dose at the discretion of the Investigator.

#### **10.3.2 Management of Allergic or Infusion-Related Reactions**

As observed with all mAbs administered by IV infusion, infusion reactions to SYNT001 are possible. In general, infusion reactions to mAbs observed in human studies typically develop

[figure not shown]
within 30 minutes to 2 hours after the initiation of drug infusion, although symptoms may be delayed for up to 24 hours. These infusion reactions can occur with the first dose of a mAb and are generally mild in severity, although severe and even fatal reactions can occur.

Allergic and/or infusion-related reactions include hypersensitivity reactions and cytokine release syndromes. These reactions are experienced by subjects during or within hours of the infusion of mAb therapy. Symptoms can include flushing, alterations in heart rate and blood pressure, dyspnea, bronchospasm, back pain, fever, urticaria, edema, nausea, and all types of rashes. Anaphylaxis is recognized as a severe, life-threatening, generalized, or systemic reaction. This is a medical emergency characterized by rapidly developing life-threatening airway and/or breathing and/or circulation problems usually associated with skin or mucosal changes.

Management of Grade 1 infusion reactions include interrupting the infusion or decreasing the rate of infusion by 50% and observing. Symptoms may also be treated as needed with medications such as diphenhydramine, hydrocortisone, or acetaminophen, either alone or in combination, depending on the subject's signs and symptoms. If the infusion is interrupted or the infusion rate is decreased, it is important to note that all study drug infusions must be completed within 4 hours of SYNT001 preparation.

[figure not shown]
Management of Grade 2 and higher infusion reactions should include stopping the infusion of study drug. Continued treatment with SYNT001 is prohibited following Grade 2 or higher infusion reactions. See [Figure 2](#) and [Figure 3](#) for details on the management of Grade 2 and Grade 3 infusion reactions. Allergic or infusion-related reactions will be graded in severity and managed based on NCI CTCAE Version 4.03 (see [Table 9](#)).

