**Figure 2. Management of Moderate (Grade 2) Infusion Reactions**

**Figure 3. Management of Severe (Grade 3 or Higher) Infusion Reactions**

**Table 9. Grading and Management of Allergic or Infusion-Related Reactions**

Adverse Event	Grade				
	1	2	3	4	5
Infusion-related reaction	Mild transient reaction; infusion interruption not indicated; intervention not indicated	Therapy or infusion interruption indicated but responds promptly to symptomatic treatment (eg, antihistamines, NSAIDs, narcotics, IV fluids); prophylactic medications indicated for ≤24 hours	Prolonged (eg, not rapidly responsive to symptomatic medication and/or brief interruption of infusion); recurrence of symptoms following initial improvement, hospitalization indicated for clinical sequelae	Life-threatening consequences; urgent intervention required	Death
Allergic reaction	Transient flushing or rash, drug fever <38.0°C. Intervention not indicated	Therapy or infusion interruption indicated but responds promptly to symptomatic treatment (eg, antihistamines, NSAIDs, narcotics, IV fluids); prophylactic medications indicated for ≤24 hours	Prolonged (eg, not rapidly responsive to symptomatic medication and/or brief interruption of infusion); recurrence of symptoms following initial improvement, hospitalization indicated for clinical sequelae (eg, renal impairment, pulmonary infiltrates)	Life-threatening consequences; urgent intervention required	Death
Anaphylaxis	–	–	Symptomatic bronchospasm, with or without urticarial; parenteral intervention indicated; allergy-related edema/angioedema; hypotension	Life-threatening consequences; urgent intervention required	Death
Cytokine release syndrome	Mild reaction; infusion interruption not indicated; intervention not indicated	Therapy or infusion interruption indicated but responds promptly to symptomatic treatment (eg, antihistamines, NSAIDs, narcotics, IV fluids); prophylactic medications indicated for ≤24 hours	Prolonged (eg, not rapidly responsive to symptomatic medication and/or brief interruption of infusion); recurrence of symptoms following initial improvement, hospitalization indicated for clinical sequelae (eg, renal impairment, pulmonary infiltrates)	Life-threatening consequences; pressor or ventilator support indicated	Death

Abstracted from NCI CTCAE Version 4.03.

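### Section 10.3.2 manages a Grade 1 infusion reaction with interruption or as-needed medication and lets the infusion finish, but Table 9 makes a reaction that needs either one Grade 2, which ends SYNT001

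*Protocol*

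**What the plan says.** All the relevant text is in the current body of the protocol, in Section 10.3.2 and Table 9.

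For Grade 1, Section 10.3.2 states: "Management of Grade 1 infusion reactions include interrupting the infusion or decreasing the rate of infusion by 50% and observing". It continues: "Symptoms may also be treated as needed with medications such as diphenhydramine, hydrocortisone, or acetaminophen, either alone or in combination". It then gives a time limit for an infusion that was paused or slowed: "all study drug infusions must be completed within 4 hours of SYNT001 preparation". So a Grade 1 infusion is meant to be completed.

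For Grade 2 and above, the next paragraph calls for the infusion to be stopped and adds: "Continued treatment with SYNT001 is prohibited following Grade 2 or higher infusion reactions".

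That paragraph also names the scale: "Allergic or infusion-related reactions will be graded in severity and managed based on NCI CTCAE Version 4.03", with a pointer to Table 9. For an infusion-related reaction, Table 9 has:

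- Grade 1: "Mild transient reaction; infusion interruption not indicated; intervention not indicated"
- Grade 2: "Therapy or infusion interruption indicated but responds promptly to symptomatic treatment"
- Grade 3: "Prolonged (eg, not rapidly responsive to symptomatic medication and/or brief interruption of infusion", among other criteria

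The full CTCAE text in Appendix 1 draws the same line between Grades 1 and 2. In Table 9, cytokine release syndrome is split the same way, and Grade 1 allergic reaction also requires that no intervention is indicated.

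**The concern.** Treatments that Section 10.3.2 offers for a Grade 1 reaction are the features that Table 9 uses to call a reaction Grade 2. Because the ban on further dosing begins at Grade 2, the grade decides whether the subject stays on drug.

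Two Investigators could see the same mild reaction, give an antihistamine because symptoms call for it, and watch it settle promptly. One would complete the infusion and dose again the next week. The other would stop SYNT001 for good. The same event would also be reported at different grades in a primary safety endpoint that is summarised by severity (Section 3.4). The stopped subject remains in follow-up (Sections 6.1 and 9.2), so the reduced exposure enters the cohort's IgG and PDAI summaries for dose selection.

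**Working it through.** There is no planned figure to reproduce. The check sets the Grade 1 paragraph of Section 10.3.2 against Table 9 for each kind of mild reaction.

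1. **Rate halved, subject observed, nothing else needed.** Section 10.3.2: Grade 1, infusion completed. Table 9: a rate cut is not named as interruption or therapy, so Grade 1. No conflict.
2. **Infusion paused purely as a precaution.** Section 10.3.2: Grade 1, infusion completed. Table 9: interruption was not indicated, so Grade 1. No conflict.
3. **Medication needed for signs or symptoms, prompt response.** Section 10.3.2: may be handled as Grade 1, infusion completed. Table 9: therapy indicated with prompt response, so Grade 2, infusion stopped, no further SYNT001. Conflict.
4. **Pause clinically necessary, prompt response.** Section 10.3.2: interruption is listed without qualification as Grade 1 management, infusion completed. Table 9: interruption indicated, so Grade 2, same stop. Conflict.
5. **Response not rapid.** Table 9: Grade 3. The Grade 1 paragraph does not reach this case.

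The conflict is confined to cases 3 and 4. Case 3 is the firmer one. Antihistamines are Table 9's first example of symptomatic treatment at Grade 2, and diphenhydramine is the first drug in the Grade 1 list of Section 10.3.2. No criterion is given to separate the two uses.

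The difference between the two readings, per affected subject, follows from the number of planned doses N (5 in Cohorts 1 and 2, 14 in Cohort 3) and the dose k at which the reaction occurs. Under the stop reading the later doses lost are N − k, and the rest of dose k is lost too. Under the continue reading none are lost.

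- N = 5: k = 1 gives 5 − 1 = 4 later doses lost, 4/5 = 80%; k = 5 gives 0.
- N = 14: k = 1 gives 14 − 1 = 13 later doses lost, 13/14 = 92.9%; k = 14 gives 0.

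One subject is 1/4 = 25% of a cohort of 4 and 1/8 = 12.5% of a cohort of 8 in the proportion of PDAI responders.

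**The case against.** The best defence is to grade first and manage second. Table 9 grades by what is indicated, not by what was done. If neither therapy nor interruption is indicated, the reaction is Grade 1, and the Grade 1 paragraph then lists precautionary or comfort measures. This stands for the precautionary pause, and the rate cut needs no rescue. It does not save medication given as needed according to the subject's signs and symptoms, which is treatment that is indicated in any ordinary sense. Nor does it explain why interruption is listed without qualification.

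Section 9.5.3 also lets an Investigator stop dosing after a related non-serious event judged unsafe to continue, so some variation between Investigators is intended. That is discretion to stop. It does not lift a prohibition on continuing.

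Figures 2 and 3 were not visible in the copy reviewed. Their titles cover Grade 2 and Grade 3 or higher, and nothing here relies on their content.

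A reader might infer more than the documents support:

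- **That prohibited medication item 4 (Section 7.12 and synopsis) is a second, independent contradiction.** It lets subjects whose earlier reaction was treated with corticosteroids receive them intravenously before an infusion, so it expects re-dosing. Because the Grade 1 paragraph itself allows hydrocortisone, the item repeats the same tension, and only if that treatment was indicated.
- **That the bar on replacing subjects withdrawn for an adverse event makes matters worse throughout.** Section 9.2 replaces only subjects withdrawn with no dose or one dose, so the bar matters only after a first-dose reaction, and a subject who stops drug but stays in follow-up is not clearly withdrawn.
- **That the dose-loss percentages, or the absence of infusion reactions in Phase 1a, size the defect.** The percentages describe any early discontinuation in a small cohort. The Phase 1a statement comes from the amendment rationale and concerns single doses in healthy volunteers, so it gives no rate for weekly dosing in patients.

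**Conclusion.** The concern holds in a bounded form. A mild, promptly settling reaction that needs medication or a necessary pause has two opposite outcomes under adjacent paragraphs of Section 10.3.2: complete the infusion and continue, or stop and never dose again. This is a continue-or-stop safety rule, so it should be corrected.

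For an affected subject the difference ranges from no later doses, if the reaction occurs at the last infusion, to 80% or 93% of planned doses if it occurs at the first. These are limits for one subject, not an expected effect on the trial, since the documents give no reaction rate in patients. The conclusion assumes that medication given because symptoms need it counts as indicated therapy under Table 9.

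It would be wrong to read this as touching the dose-escalation or study stopping rules. The DLT rule in Section 9.5.1 uses Grade 3 events and the suspension rule in Section 9.5.2 uses Grade 4 events, so neither depends on the line between Grades 1 and 2. Prophylaxis under permitted item 5 of Section 7.12 is also unaffected.

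**What to change.** In Section 10.3.2:

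- State that Table 9 alone sets the grade.
- Limit Grade 1 management to a 50% rate reduction or a purely precautionary pause, with observation.
- Remove the sentence on as-needed medication from the Grade 1 paragraph.
- State that a reaction for which medication or interruption is indicated is Grade 2 and that SYNT001 is then stopped.

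Align the corticosteroid exception in prohibited item 4 of Section 7.12 and the synopsis. Once these changes are made, a reaction for which corticosteroids were indicated ends dosing, so the exception has no one left to cover.

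The cost is a few sentences by amendment, IRB submission under Section 12.4 and a note to sites, with no change to data collection or analysis. The small downside is that some mild, medicated reactions will end dosing.

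If the sponsor instead wants re-dosing after promptly resolving Grade 2 reactions, both the ban on continued treatment and the separate instruction to stop the infusion at Grade 2 must be changed. That loosens a safety rule and needs its own stated justification.

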**Figure 2. Management of Moderate (Grade 2) Infusion Reactions**

**Figure 3. Management of Severe (Grade 3 or Higher) Infusion Reactions**

**Table 9. Grading and Management of Allergic or Infusion-Related Reactions**

Adverse Event	Grade				
	1	2	3	4	5
Infusion-related reaction	Mild transient reaction; infusion interruption not indicated; intervention not indicated	Therapy or infusion interruption indicated but responds promptly to symptomatic treatment (eg, antihistamines, NSAIDs, narcotics, IV fluids); prophylactic medications indicated for ≤24 hours	Prolonged (eg, not rapidly responsive to symptomatic medication and/or brief interruption of infusion); recurrence of symptoms following initial improvement, hospitalization indicated for clinical sequelae	Life-threatening consequences; urgent intervention required	Death
Allergic reaction	Transient flushing or rash, drug fever <38.0°C. Intervention not indicated	Therapy or infusion interruption indicated but responds promptly to symptomatic treatment (eg, antihistamines, NSAIDs, narcotics, IV fluids); prophylactic medications indicated for ≤24 hours	Prolonged (eg, not rapidly responsive to symptomatic medication and/or brief interruption of infusion); recurrence of symptoms following initial improvement, hospitalization indicated for clinical sequelae (eg, renal impairment, pulmonary infiltrates)	Life-threatening consequences; urgent intervention required	Death
Anaphylaxis	–	–	Symptomatic bronchospasm, with or without urticarial; parenteral intervention indicated; allergy-related edema/angioedema; hypotension	Life-threatening consequences; urgent intervention required	Death
Cytokine release syndrome	Mild reaction; infusion interruption not indicated; intervention not indicated	Therapy or infusion interruption indicated but responds promptly to symptomatic treatment (eg, antihistamines, NSAIDs, narcotics, IV fluids); prophylactic medications indicated for ≤24 hours	Prolonged (eg, not rapidly responsive to symptomatic medication and/or brief interruption of infusion); recurrence of symptoms following initial improvement, hospitalization indicated for clinical sequelae (eg, renal impairment, pulmonary infiltrates)	Life-threatening consequences; pressor or ventilator support indicated	Death

Abstracted from NCI CTCAE Version 4.03.

### 10.3.3 Potential Immune Effects

An antibody blocking FcRn is anticipated to have several effects. These include acceleration of catabolism of IgG, but not other immunoglobulin isotypes such as IgA and IgM, leading to dose-dependent decreases in circulating IgG levels by up to an estimated 50% from the baseline levels after a single dose and further decreases after multiple doses up to a 70% to 80% reduction. Based on studies in humans, it is expected that with a single dose, the nadir of this effect will

occur approximately 5 days after dosing. The time course of recovery of IgG following dosing in the Phase 1a study suggests that a return to within 30% of baseline levels observed at pretreatment occurs within 4 weeks after a single dose and within 4 weeks after multiple doses as shown in NHPs.

Given the normal adult range of total IgG of 500 to 1600 mg/dL (Agarwal and Cunningham-Rundles, 2007; Furst, 2009; Gonzalez-Quintela et al., 2008; Jolliff et al., 1982; Keystone et al., 2007; McMillan et al., 1997; van Vollenhoven et al., 2013), with a mean of 1150 mg/dL, a 50% decrease in the mean would be to 575 mg/dL and a 50% decrease from the low end of the normal range used for the inclusion criteria of 600 mg/dL in this study would be to 300 mg/dL. An 80% decrease from baseline after multiple doses would result in IgG levels of 230 mg/dL and 120 mg/dL, respectively. While these levels are in the range found in patients with primary humoral immunodeficiency (Ameratunga et al., 2013), the levels will be transient. Further, as reported for other therapies used for pemphigus, the temporary (ie, less than 4 months) depletion of IgG (up to 95% reduction of total IgG as seen with immunoadsorption) does not appear to impart an increased risk of infection (Eming and Hertl, 2006; Furst, 2009; Keystone et al., 2007; Schmaldienst et al., 2001; van Vollenhoven et al., 2013). Study subjects will be monitored clinically for any infection. Further, commercial IVIG can be given to reverse the low IgG levels in case of a bacterial infection occurring while their IgG levels are decreased.

An antibody that blocks FcRn is expected to also down-modulate innate and adaptive immunity and the catabolism of IgG-containing immune complexes (IC). Specifically, it is expected that anti-FcRn will promote the clearance of IgG-containing ICs and the effects of these ICs on stimulating innate immune cell production of inflammatory cytokines (eg, interleukin 12 [IL-12], interferon- $\gamma$ , and tumor necrosis factor [TNF]) and inhibit the processing and presentation of antigens contained within ICs and thus the antigen-specific activation of CD4+ and CD8+ T-cells. Therefore, subjects with pre-existing conditions that are dependent upon IgG antibodies, such as chronic infections (eg, HIV, HBV or HCV), will be excluded from this study, as will subjects with active infection, in general.

